### 6.5.1 Overview of Immunogenicity Analyses

Table 7 presents an overview of the immunogenicity analyses that will be performed. A table summarizing the disposition of participants for immunogenicity samples will be provided for each immunogenicity assay.

**Table 7 Overview of Primary, Secondary and Exploratory Immunogenicity Analyses**

Laboratory/Assay	Reference to Phase 1/2/3a Protocol Endpoints	Summary Level	Main/Supportive	Variant/antigen	Analyzed Time-points	Analysis Set (a) (b)	Subgroup
NIHE/NAb by sVNT	Primary	SC rate	Main	Ancestral	Day 57	Phase 1/2/3a IAS (Two dose schedule)	Yes
NIHE/NAb by sVNT	Secondary 1	GMC; GMFR; SC rate	Main	Ancestral	Day 1, Day 29, Day 57, Day 92	Phase 1/2/3a IAS (Two dose schedule)	Yes
NIHE/IgG bAb	Secondary 1	GMC; GMFR; SC rate	Main	Ancestral	Day 1, Day 29, Day 57, Day 92	Phase 1/2/3a IAS (Two dose schedule)	Yes
PPD/IgG bAb by MSD multiplex (c)		GMC; GMFR; SC rate	Supportive for Secondary endpoint 1 (Serum IgG bAb)	Ancestral	Day 1, Day 57	Phase 1/2 IAS (Two dose schedule)	
NIHE/NAb by PRNT50	Secondary 2	GMC; GMFR; SC rate	Main	Ancestral-clinical isolate variant (ancestral variant)	Day 1, Day 29, Day 57	Phase 1/2 IAS (Two dose schedule)	
NIHE/NAb by PRNT50	Exploratory (d)	GMC; GMFR; SC rate	Main	Delta-clinical isolate variant	Day 1, Day 57	Phase 1 IAS	
PPD/NAb by ACE2/sVNT	Exploratory 3	GMC; GMFR; SC rate	Main	S_S_B.1.1.7, S_B.1.351, S_B.1.526.1, S_B.1.617, S_B.1.617.1, S_B.1.617.2, S_B.1.617.3, S_P1, S_P2	Day 1, Day 57	Phase 1/2 IAS (Two dose schedule)	
PPD/NAb by ACE2/sVNT	Exploratory (d)	GMC; GMFR; SC rate	Main	S_S_B.1.1.7, S_B.1.351, S_B.1.526.1, S_B.1.617, S_B.1.617.1, S_B.1.617.2, S_B.1.617.3, S_P1, S_P2	Day 1, Day 57	Phase 1 IAS	

Laboratory/Assay	Reference to Phase 1/2/3a Protocol Endpoints	Summary Level	Main/Supportive	Variant/antigen	Analyzed Time-points	Analysis Set (a) (b)	Subgroup
PPD/NAb by MNT	Exploratory 3,4	GMC; GMFR; SC rate	Main	D614G	Day 1, Day 57, Day 92, Day 120	Phase 1/2/3a IAS (Two dose schedule) Phase 2/3a IAS (Three dose schedule) Phase 1 IAS	
	Exploratory 3,4	GMC; GMFR; SC rate		Delta	Day 1, Day 57, Day 92, Day 120	Phase 2/3a IAS (Two dose schedule) Phase 2/3a IAS (Three dose schedule)	
	Exploratory 3,4	GMC; GMFR; SC rate		Omicron BA.1	Day 1, Day 57, Day 92, Day 120	Phase 2/3a IAS (Two dose schedule) Phase 2/3a IAS (Three dose schedule)	
NIHE/NAb by sVNT	Exploratory 5	GMC; GMFR; SC rate	Main	Ancestral	Day 1, Day 29, Day 57, Day 92, D120	Phase 2/3a IAS (Three dose schedule)	
NIHE/NAb by sVNT	Exploratory (d)	GMC; GMFR; SC rate	Main	Ancestral	Day 1, Day 29, Day 57, Day 92	Phase 1 IAS	
NiHE/IgG bAb	Exploratory 6	GMC; GMFR; SC rate	Main		Day 1, Day 57, Day 92, Day 120	Phase 2/3a IAS (Three dose schedule)	
NIHE/IgG bAb	Exploratory (d)	GMC; GMFR; SC rate	Main		Day 1, Day 57, Day 92	Phase 1 IAS	

(a) IAS includes all participants who received all protocol-required doses of study vaccine (ARCT-154 or placebo) up to the evaluation timepoint concerned. Two Dose Schedule or Three Dose Schedule means that IAS for the analysis of the endpoint includes participants who received the first two or three doses of study vaccine, respectively.

(b) sensitivity analyses will be performed on the PP set (immunogenicity) for the same pooling as IAS.

(c) Assessment of serum IgG bAb by MSD multiplex assessment is not a secondary objective but is considered as a supportive analysis for the secondary objective Serum IgG bAb (by NIHE). (d) As per protocol, no immunogenicity objectives are defined so immunogenicity analyses performed on phase 1 are considered exploratory.

### 6.5.2 Neutralizing antibody (NAb) responses to ARCT-154 by surrogate virus neutralization test (sVNT)

Neutralizing antibody (NAb) responses by surrogate virus neutralization test (sVNT) as performed by National Institute of Hygiene and Epidemiology, Department of Virology, Vietnam (NIHE), evaluated at Day 1 (baseline) and Day 57 for assessment of seroconversion (based on seroconversion FDA definition provided in section 6.5) in all participants in the Phase 1/2/3a IAS is considered as the Phase 1/2/3a Substudy Primary Immunogenicity Objective (Primary Immunogenicity estimand as described in appendix 9.2). The hypotheses to be tested are described in section 6.2.3.

The number and proportion (and its 95% CI) of participants achieving seroconversion at Day 57 will be provided for each treatment. The two-sided 95% CI of the seroconversion rate will be calculated using the Clopper-Pearson method. In addition, the treatmentdifference, ARCT-154-Placebo, in proportion of participants achieving seroconversion at Day 57 will be provided, along with corresponding two-sided 95% CI (calculated using the Miettinen and Nurminen method)

The following formula, which is provided in the assay kit by the manufacture, will be used for converting sVNT NAb titer (U/mL) to standard unit (IU/mL):

$$\text{Result (IU/mL)} = \text{Result (NAb titer)} / 12.3$$

Neutralizing antibody (Nab) responses by sVNT as performed by NIHE will also be evaluated by GMC, GMFR (not applicable for Day 1), and seroconversion rate (not applicable for Day 1) for the following analysis sets and timepoints where applicable:

- Phase 1 IAS: Day 1, Day 29, Day 57, Day 92.
- Phase 1/2/3a IAS: Day 1, Day 29, Day 57, Day 92 (Phase 1/2/3a Substudy Secondary Immunogenicity Objective)
- Phase 2/3a IAS: Day 1, Day 29, Day 57, Day 92, Day 120 (Phase 1/2/3a Substudy Exploratory Immunogenicity Objective)

Neutralizing antibody (Nab) responses by sVNT, as performed by PPD Laboratories, USA, (Angiotensin-converting enzyme 2 (ACE2)/sVNT) will be evaluated by GMC, GMFR, and seroconversion rate for the following analysis sets and timepoints where applicable:

- Phase 1 IAS: Day 1, Day 57.
- Phase 1/2 IAS: Day 1, Day 57 (Phase 1/2/3a Substudy Exploratory Immunogenicity Objective)

Supportive analyses will be performed in the corresponding per protocol (PP) immunogenicity sets. Subgroup analyses will be performed as described in section 6.5.7.

### 6.5.3 Early neutralizing antibody responses using a live virus assay: NAb responses by plaque reduction neutralization test at 50% reduction (PRNT50)

NAb responses by plaque reduction neutralization test at 50% reduction (PRNT50), as performed by NIHE will be evaluated for immune responses to SARS-CoV-2 D614G variant by GMC, GMFR, and seroconversion rate for the following analysis sets and timepoints where applicable:

- Phase 1 IAS: Day 1 (baseline), Day 29 and Day 57.
- Phase 1/2 IAS: Day 1 (baseline), Day 29 and Day 57 (Phase 1/2/3a Substudy Secondary Immunogenicity Objective)

Sensitivity analyses will be performed in the per protocol (PP) immunogenicity sets.

NAb responses by plaque reduction neutralization test at 50% reduction (PRNT50), as performed by NIHE will be evaluated for immune responses to SARS-CoV-2, Delta variant by GMC, GMFR, and seroconversion rate for the following analysis sets and timepoints where applicable:

- Phase 1 IAS: Day 1 (baseline), Day 29 and Day 57.
- Phase 1/2 IAS: Day 1 (baseline), Day 29 and Day 57 (Phase 1/2/3a Substudy Exploratory Immunogenicity Objective)

Sensitivity analyses will be performed in the per protocol (PP) immunogenicity sets.

### 6.5.4 IgG antibody binding the SARS-CoV-2 spike protein (binding antibody [BAb])

IgG antibody binding the SARS-CoV-2 spike protein (binding antibody [BAb]), as performed by NIHE will be evaluated for assessment of by GMC, GMFR, and seroconversion rate for the following analysis sets and timepoints where applicable:

- Phase 1 IAS: Day 1, Day 29, Day 57, Day 92
- Phase 1/2/3a IAS: Day 1, Day 29, Day 57, Day 92 (Phase 1/2/3a Substudy Secondary Immunogenicity Objective)
- Phase 2/3a IAS: Day 1, Day 29, Day 57, Day 92, Day 120 (Phase 1/2/3a Substudy Exploratory Immunogenicity Objective)

Sensitivity analyses will be performed in the per protocol (PP) immunogenicity sets.

### 6.5.5 Neutralizing antibody (NAb) responses to ARCT-154 by pseudovirus microneutralization test (MNT)

NAb responses by microneutralization test (MNT), as performed by PPD Laboratories, USA, will be evaluated for immune responses to SARS-CoV-2 variants, including D614G (VAC62), Delta (VAC120) and Omicron BA.1 (VAC122) variants by GMC, GMFR, and seroconversion rate for the following analysis sets and timepoints where applicable:

- D614G VAC62 (validated):
  - Phase 1 IAS: Day 1 and Day 57
  - Phase 1/2/3a IAS: Day 1 and Day 57, Day 92 (Phase 1/2/3a Substudy Exploratory Immunogenicity Objective)
  - Phase 2/3a IAS: Day 1 and Day 57, Day 92 and D120 (Phase 1/2/3a Substudy Exploratory Immunogenicity Objective)
- Delta VAC120 (validated):
  - Phase 2/3a IAS: Day 1 and Day 57, Day 92 and D120 (Phase 1/2/3a Substudy Exploratory Immunogenicity Objective)
- Omicron BA.1 VAC122 (validated):
  - Phase 2/3a IAS: Day 1 and Day 57, Day 92 and D120 (Phase 1/2/3a Substudy Exploratory Immunogenicity Objective)

Sensitivity analyses will be performed in the per protocol (PP) immunogenicity sets.

For D614G VAC62, the following formula will be used for converting results in AU/mL into standard units (IU/mL): AU/mL is 1 IU/mL = 1.275 AU/mL. Results in both units will be presented.

### **6.5.6 Serum IgG antibodies binding the SARS-CoV-2 spike by Mesoscale Discovery (MSD) multiplex assay**

IgG antibody binding the SARS-CoV-2 spike protein (binding antibody [BAb]) by Mesoscale discovery (MSD) multiplex assay, as performed by PPD Laboratories, USA, will be assessed for immune response by GMC, GMFR, and seroconversion rate in the following analysis sets and timepoints where applicable:

- Phase 1 IAS: at Day 1 and Day 57
- Phase 1/2 IAS: at Day 1 and Day 57

In addition, the number and proportion (along with two-sided exact Clopper-Pearson 95% CI) of participants demonstrating seropositivity, defined as BAb by MSD multiplex Nucleocapsid (VAC72 N) > 5000 AU/mL will be summarized by timepoint and treatment arm (as exploratory analysis).

Sensitivity analyses will be performed in the per protocol (PP) immunogenicity sets.

### **6.5.7 Immunogenicity Analysis by subgroups**

To assess the consistency of immunogenicity across various subgroups in Phase 1/2/3a, the following immunogenicity analyses will be performed in the subgroups listed in section 6.2.5.

The following analysis will be repeated by subgroup:

- Neutralizing antibody (NAb) responses by surrogate virus neutralization test (sVNT) as performed by NIHE (seroconversion rate) in Phase 1/2/3a IAS analysis set: Day 1, Day 29, Day 57, Day 92
- IgG antibody binding the SARS-CoV-2 spike protein (binding antibody [BAb]), as performed by NIHE (seroconversion rate) in Phase 1/2/3a IAS: Day 1, Day 29, Day 57, Day 92

## 6.6 Safety Evaluations

Main estimation of primary safety endpoint for Phase 1/2/3a, 3b, and 3c are described by estimands 3 and 4. Refer to section 9.2.2 for description of those estimands. Pooled data from Phase 1/2/3a/3b will also be presented.

### 6.6.1 Adverse Events

In this study, AEs include subcategories of AEs collected by solicitation of participants as to types of signs and symptoms observed following vaccination (reactogenicity), referred to as “solicited AEs”, and a general category of unsolicited AEs that includes any spontaneously reported or observed AE occurring after the signing of informed consent. Further definitions are provided in section 6.6.1.1 and 6.6.1.2.

An overview of main and supportive analyses for safety endpoints is provided in Table 8.

All adverse events that started on or after first vaccination date (Day 1) will be classified as treatment emergent adverse events (TEAEs). For events occurring on the day of first vaccination, an AE will be considered emergent if the investigator indicated on the CRF that the AE occurred after the vaccination. If there is not enough evidence to identify whether an AE occurred before or after the first injection, the AE will be considered as a TEAE. In addition, if an AE onset date or time is missing, or partially missing, and it cannot be determined whether the AE started during a specific reporting interval, it will be considered for the reporting of this interval, unless the end date indicates that the event ended before the interval started.

For participants with more than one episode of the same event, the event of greatest severity and relationship will be used in any summary, while retaining individual records of the episodes in the dataset.

Handling of solicited and unsolicited events of participants who received incorrect study vaccine is described in section 4.1.

**Table 8 Overview of Safety Endpoints**

	Description	Analysis Set and timepoint
--	-------------	----------------------------

Solicited AEs	Occurrence of solicited AEs within 7 days after each study vaccine administration	Phase 1/2/3a RAS: after Day 1 and Day 29 doses Phase 3b RAS: after Day 1 and Day 29 doses Phase 2/3a RAS: After Day 92 Phase 3c RAS: after Day 1 and Day 29 doses Pooled RAS: after Day 1 and Day 29 doses
	Occurrence of solicited AEs within 30 minutes after each study vaccine administration. Occurrence of solicited AEs by grade	Phase 1/2/3a RAS: after Day 1 and Day 29 doses Phase 3b RAS: after Day 1 and Day 29 doses Phase 2/3a RAS: After Day 92 DosePhase 3c RAS: after Day 1 and Day 29 doses Pooled RAS: after Day 1 and Day 29 doses
Unsolicited AEs	Occurrence of unsolicited AEs up to 28 days after each study vaccine administration up to Day 92 (dose 1, dose 2)	Phase 1/2/3a SAS Phase 3b SAS Phase 3c SAS Pooled SAS
	Occurrence of unsolicited AEs up to 28 days after each study vaccine administration after switchover/receipt of further study vaccine	Phase 1/2/3a SAS Phase 3b SAS Pooled SAS
SAEs, MAAEs, AEs leading to discontinuation of treatment, AEs leading to discontinuation of Study	Occurrence of AEs leading to discontinuation, MAAEs, or SAEs up to Day 92 or Switchover/Further Study Vaccine or receipt of non-study COVID-19 vaccine	Phase 1/2/3a SAS Phase 3b SAS Phase 3c SAS Pooled SAS

	Occurrence of AEs leading to discontinuation, MAAEs, or SAEs in other time intervals	Phase 1/2/3a SAS Phase 3b SAS Phase 3c SAS Pooled SAS
--	--	--

### 6.6.1.1 Solicited Adverse Events (Reactogenicity)

The term “reactogenicity” refers to selected signs and symptoms (“reactions”) occurring in the hours and days following a vaccination. These signs and symptoms are collected as solicited AEs from participants during the 30 minute observation period after vaccination and by use of the Diary for 7 consecutive days following each study vaccine administrations. The following solicited AEs are included in the Diary:

- **Solicited local AEs:** injection site erythema, injection site pain, injection site induration/swelling, and injection site tenderness
- **Solicited systemic AEs:** arthralgia, chills, diarrhea, dizziness, fatigue, fever (categorized by measured body temperature), headache, myalgia, and nausea, vomiting

Solicited AEs are captured in the following way:

- Participant’s data recorded directly on the Diary (paper or eDiary, primary analysis)
- Investigator’s re-assessed data

Analysis of reactogenicity data will be performed based on the participant’s data recorded on the Diary/eDiary.

Reactogenicity will be analyzed after each vaccine dose (within 30 minutes or during first 7 days after the dose - refer to Table 8 for timepoints available). Participants will be considered for the computation of percentages in the specified time interval if they received the study vaccine and provided at least 1 reactogenicity diary report in the specified interval. Participants whose data are completely missing within the summary of event and timepoint (i.e no answer to a reaction category for the specific timepoint) will not be included in both numerator and denominator. For each time interval and reaction category the number of participants without missing data will be presented.

Severity of solicited local and systemic reactions will be graded as follows: grade 0 (none), grade 1 (mild), grade 2 (moderate), grade 3 (severe), and grade 4 (potentially life threatening). For participants with more than one episode of the same event in a reporting period, the event of greatest severity will be used in any summary.

Presence of a local/systemic reaction within the 30 minute observation period following each vaccination is defined as the reaction recorded in the CRF with a severity grade of 1 or higher on the analysis time point. Presence of any local/systemic reaction within 30 minute observation period following each vaccination is defined as participant reports at least one local or systemic reaction within 30 minute observation period.

Presence of each local/systemic reaction within 7 days after each dose of study vaccine is defined as participant reports the reaction as “yes” on the analysis time point in the diary. Presence of any local/systemic reaction within 7 days after each dose is defined as participant reports the reaction as “yes” in the diary for at least one local or systemic reaction.

The number and proportion of participants experiencing solicited events will be presented as follows:

- Overview of Reactions within 30 minutes after each dose:
  - at least one reaction (local or systemic), at least one local reaction, at least one systemic reaction
  - At least one reaction, by reaction
- Summary of reactions within 30 minutes after each dose by grade:
  - one reaction (local or systemic), at least one local reaction, at least one systemic reaction
  - At least one reaction, by reaction
- Overview of Reactions within 7 days after each dose:
  - at least one reaction (local or systemic), at least one local reaction, at least one systemic reaction
  - At least one reaction, by reaction
- Summary of reactions within 7 days after each dose by grade:
  - one reaction (local or systemic), at least one local reaction, at least one systemic reaction
  - At least one reaction, by reaction
- Summary of first onset of reaction within 7 days after each dose by day of occurrence:
  - at least one reaction (local or systemic), at least one local reaction, at least one systemic reaction
  - At least one reaction, by reaction
- Summary of any reactions within 7 days after each dose by day of occurrence:
  - at least one reaction (local or systemic), at least one local reaction, at least one systemic reaction
  - At least one reaction, by reaction

Each of the analysis above will be displayed in the following analysis set and timepoint:

Analysis set	Timepoint
Phase 1/2/3a RAS	After Dose 1, after Dose 2, after Dose 1 or 2
Phase 2/3a RAS	After Dose 3

	Any dose (Dose 1, 2 and 3)
Phase 3b RAS	After Dose 1, after Dose 2, after Dose 1 or 2
Phase 3c RAS	After Dose 1, after Dose 2, after Dose 1 or 2
Pooled RAS	After Dose 1, after Dose 2, after Dose 1 or 2

Overview tables for Phase 3b RAS will be also produced by subgroups as specified in Section 6.2.5.

For outputs by grade, bar plots will be produced displaying percentage of participants with each grade.

Median time of onset and median duration of local and systemic reactions will be summarized for Phase 1/2/3a RAS, Phase 3b RAS, Phase 3c RAS, and Pooled RAS after Dose 1 or 2.

All solicited AEs occurring on study will be listed in participant data listings using the randomized set. In addition, solicited AEs occurring in the set of participants who received at least one incorrect dose of study vaccines will be provided.

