4.5.5 Additional Procedural Specifics

4.5.5.1 Diary Use to Collect Solicited Adverse Events

A Diary (electronic or paper if electronic is not feasible) will be used to collect solicited AEs (i.e., reactogenicity) directly from the participant:

- Solicited local and systemic AEs will be recorded daily for 7 days starting on the day of each study vaccination in the primary vaccination series (Day 1 and 29). For participants in Phase 2 and 3a, solicited AEs will also be recorded daily for 7 days following the 3rd injection (Day 92).
 - Solicited local AEs include injection site erythema, injection site pain, injection site induration/swelling, and injection site tenderness.
 - Solicited systemic AEs include arthralgia, chills, diarrhea, dizziness, fatigue, fever (categorized by measured body temperature), headache, myalgia, and nausea/vomiting.
 - Also solicited but not categorized as AEs are antipyretic and analgesic use.
 - All participants will be trained on what information will be collected from them following each vaccination. This includes how to evaluate and score each solicited AE. Some solicited AEs are not scored directly by the participant, but the values recorded will be analyzed for severity including body temperature and visible injection site reactions (erythema or induration/swelling). Body

temperature and visible injection site reactions will be measured daily by thermometer and ruler, respectively, provided by the site. Participants should be trained on how to use the thermometer (including capture of highest body temperature if the participant perceives the onset of possible fever) and the ruler. Participants should be encouraged to complete the diary at roughly the same time of day for the 7 days following vaccination when recording the solicited AEs.

- An electronic Diary (eDiary) will involve the use of an application on the individual participant's mobile phone or through the use of a loaner mobile phone with the application installed. If an eDiary is not feasible, then a paper diary will be used by the participant. Training on how to use either the electronic or paper diary will be performed at the time of the Day 1 visit. The eDiary will use prompts to encourage the participant to enter data, alerts to inform the site and other team members of potential toxicity grade solicited AEs (if relevant). Timely follow-up of these alerts is expected.

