APPENDIX 4: TOXICITY GRADING SCALES

Table 19 Toxicity Grading for Solicited Adverse Events

Solicited Local Adverse Events	Grade 0	Grade 1 (Mild)	Grade 2 (Moderate)	Grade 3 (Severe)	Grade 4 (Potentially Life Threatening)
Injection Site Erythema *	<2.5 cm	2.5-5 cm	5.1-10 cm	>10 cm	Emergency Room (ER) visit, hospitalization or necrosis or exfoliative dermatitis
Injection Site Induration/Swelling **	<2.5 cm	2.5-5 cm	5.1-10 cm	>10 cm	ER visit or hospitalization or necrosis
Injection Site Pain	None	Present but does not interfere with daily activity	Interferes with daily activity or leads to use of non-narcotic pain reliever for >24 hours	Prevents daily activity or leads to use of narcotic pain reliever	ER visit or hospitalization
Injection Site Tenderness	None	Mild discomfort to touch	Discomfort with movement	Significant discomfort at rest	ER visit or hospitalization
Solicited Systemic Adverse Events					
Fever (°C) *** (°F) ***	<38.0 <100.4	38.0-38.4 100.4-101.1	38.5-38.9 101.2-102.0	39.0-40 102.1-104	>40 >104
Nausea/vomiting	None	1-2 episodes/24 hours	>2 episodes/24 hours without seeking medical attention	Requires outpatient intravenous hydration	ER visit or hospitalization for hypotensive shock
Diarrhea	<2 loose stools/24 hours	2-3 loose stools/24 hours	4-5 stools/24 hours	6 or more loose or watery stools/24 hours or requires outpatient intravenous hydration	ER visit or hospitalization

Table 19 Toxicity Grading for Solicited Adverse Events

Solicited Local Adverse Events	Grade 0	Grade 1 (Mild)	Grade 2 (Moderate)	Grade 3 (Severe)	Grade 4 (Potentially Life Threatening)
Headache	None	Present but without interference with daily activity	Interferes with daily activity or leads to use of non-narcotic pain reliever for >24 hours	Prevents daily activity or leads to use of narcotic pain reliever	ER visit or hospitalization
Fatigue	None	Present but without interference with daily activity	Interferes with daily activity	Prevents daily activity	ER visit or hospitalization
Myalgia	None	Present but without interference with daily activity	Interferes with daily activity	Prevents daily activity	ER visit or hospitalization
Arthralgia, chills, and dizziness	None	Present but without interference with daily activity	Interferes with daily activity	Prevents daily activity	ER visit or hospitalization

Abbreviation: ER=emergency room

* In addition to grading the measured local reaction at the greatest single diameter, the measurement should be recorded as a continuous variable.

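### SAP 6.6.1.1 counts a 7-day solicited reaction on a diary 'yes' with no grade condition, so for erythema, swelling, fever and diarrhea the presence tables need not agree with the by-grade tables

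*SAP*

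**What the plan says.** SAP 6.6.1.1 defines presence separately for the two observation windows.

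- **30 minutes, each reaction:** "the reaction recorded in the CRF with a severity grade of 1 or higher on the analysis time point".
- **7 days, each reaction:** presence "within 7 days after each dose of study vaccine is defined as participant reports the reaction as" 'yes' in the diary. For any reaction, the rule is a 'yes' "in the diary for at least one local or systemic reaction". Neither has a grade, size or temperature condition.

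The same section says reactions will be "graded as follows: grade 0 (none), grade 1 (mild), grade 2 (moderate), grade 3 (severe), and grade 4 (potentially life threatening"). It plans four kinds of 7-day output: an overview, a summary by grade, first onset by day and any occurrence by day. Bar plots by grade and median time of onset and duration are added.

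The cut-offs are in Protocol Appendix 4, Table 19 ("Toxicity Grading for Solicited Adverse Events"). Protocol 4.5.5.1 explains how measured reactions are handled: "Some solicited AEs are not scored directly by the participant, but the values recorded will be analyzed for severity including body temperature". It names visible injection-site reactions alongside temperature. The protocol's reactogenicity endpoint is solicited events within 7 days by toxicity grade.

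**The concern.** Reactogenicity is part of the primary safety objective in every phase. Readers will expect the percentage with a given reaction to equal the sum of Grades 1 to 4 in the companion table, and the 30-minute and 7-day rates to be on one scale. As written, neither is assured for reactions where Grade 0 covers real but small findings.

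The presence rule also feeds the first-onset and by-day tables, and can affect onset time and duration. Redness that shrinks from 4 cm to 1 cm may stay 'yes' after it has become Grade 0, so duration may change even for someone who clearly had a reaction. The protocol treats all solicited events as vaccine-related by definition, so whatever counts as present also counts as related.

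**Working it through.** The plan states no reaction rate to reproduce, so this is a check of definitions.

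**Step 1: which reactions can be affected.** Table 19 gives Grade 0 as simply 'None' for pain, tenderness, nausea/vomiting, headache, fatigue, myalgia, arthralgia, chills and dizziness. For these, a 'yes' should mean Grade 1 or more. Four reactions have a threshold instead:

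- erythema: under 2.5 cm
- induration/swelling: under 2.5 cm
- fever: under 38.0 °C
- diarrhea: fewer than 2 loose stools in 24 hours

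**Step 2: apply each rule at the boundary.** The last column applies the 30-minute criterion to the same value.

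| Diary entry | 7-day rule | Table 19 | 30-minute criterion |
|---|---|---|---|
| Erythema 2.4 cm, 'yes' | present | Grade 0 | absent |
| Swelling under 2.5 cm, 'yes' | present | Grade 0 on diameter | absent if Grade 0 |
| Fever 'yes', 37.9 °C | present | Grade 0 | absent |
| Fewer than 2 loose stools, 'yes' | present | Grade 0 | absent |
| Erythema 2.5 cm or 38.0 °C, 'yes' | present | Grade 1 | present |
| Fever 'no', 38.6 °C | absent | Grade 2 | present |

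The rules agree at and above the cut-off when the answer is 'yes'. They part below it. They also part in the last row, provided grading does not itself depend on a 'yes'.

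**Step 3: the gap between tables.** For one reaction, using each participant's highest grade in the window:

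overview count − sum of Grades 1 to 4 = (number 'yes' with Grade 0) − (number 'no' with Grade 1 or more)

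The two terms have opposite signs, so the direction of the net gap is not fixed. If grading is done only on 'yes' answers, the second term is zero and the overview can only be the larger count.

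**Step 4: scale.** The documents give neither term. Phase 3b plans about 8,000 ARCT-154 participants. As an assumption only, if 1% to 5% of them had only sub-threshold 'yes' answers for a reaction:

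- 0.01 × 8,000 = 80 participants, 1 percentage point
- 0.05 × 8,000 = 400 participants, 5 percentage points

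**Step 5: is it reconciled elsewhere?** SAP Section 7.1 says reactogenicity is participant-reported and is analyzed unmodified. That entry concerns intercurrent events. Nothing in Section 7 says how a 'yes' that grades as 0 is displayed.

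**The case against.** The strongest reply is that the diary form is not in the documents. Participants are trained to evaluate and score each event. Fever is categorized by measured temperature, so its 'yes' may come from the reading. If the form accepted 'yes' only at or above the cut-off, there would be no mismatch. This stands as a limit: the rows in the table are possible cases, not observed ones, and fever is less certain than redness. But neither document states such a restriction, and the 7-day rule exempts no reaction.

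Second, the protocol endpoint is already by grade and a by-grade table is planned. The yes/no overview counts everything participants perceive, which is the inclusive direction for safety. That is a defensible choice, but it does not explain why the same finding is present in one table and none in another.

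Third, the reach is limited. With the related vaccine ARCT-021, Protocol 2.6 reports that over 90% had a solicited event and that the commonest were pain, tenderness, headache, fatigue, myalgia, arthralgia and chills. None of these is among the four. If ARCT-154 behaves alike, the composite any-reaction rate in that arm should move little. This is fair.

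Fourth, deriving presence from measurements alone would not follow the protocol. The Table 19 footnote grades swelling on a functional scale as well as by size, and some higher grades rest on care received or tissue damage rather than size or count. This is right, and the fix below allows for it.

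A reader might also infer that the protocol itself requires Grade 1 or more for a reaction to be present. It does not: it supplies a severity scale and no presence rule. The explicit Grade 1 condition is only in the SAP's 30-minute rule for each reaction. The 30-minute rule for any reaction speaks only of the participant reporting at least one.

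**Conclusion.** The inconsistency is real and internal to SAP 6.6.1.1. Followed as written, for erythema, induration/swelling, fever and diarrhea, the 7-day presence outputs can count as a reaction what the by-grade table calls none, and nothing in the plan reconciles the two. It should be settled because it touches a primary safety endpoint and the remedy is small.

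The size is unknown. The firm arithmetic is that each 1% of Phase 3b ARCT-154 recipients is 80 people; the 1% to 5% range is an assumption. A reader might infer that erythema rates will be overstated by several points or by a multiple of the true rate, or that measured fevers will be missed. The documents support neither, since they give no sub-threshold or discordant rates and do not show the diary. Safety has no hypothesis test, so no formal conclusion of the trial depends on this.

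**What to change.** In SAP 6.6.1.1, for these four reactions:

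- Define 7-day presence as Grade 1 or higher under the full Table 19 criteria: the recorded measurement or stool count, the functional scale for swelling, and the care-based and other non-measurement criteria for the higher grades.
- Apply this to all 7-day overview, by-day, first-onset, onset-time and duration outputs.
- Show 'yes, Grade 0' as its own row or listing, so that the tables reconcile and stay comparable with the interim analyses.
- List measured Grade 1+ values answered 'no'.
- Record the change in SAP Section 7, noting that Phase 1/2/3a/3b data had already been unblinded for the analyses described in SAP 2.5.

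If the diary did restrict 'yes' to values at or above the cut-off, a sentence saying so would remove the sub-threshold mismatch.

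The cost is SAP wording and derivation code, provided the measurements were recorded as Protocol 4.5.5.1 requires. The downside is that small participant-perceived reactions leave the headline rate, and rates may differ slightly from the interim report. SAP 2.1 intends methods consistent with the earlier SAPs, which is why the separate row matters.
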